7.4.7 Randomisation

Randomisation lists will be generated using block randomisation with random variable block length, stratified by site and MS type, and a 1:1 randomisation ratio.

Lists will be produced by an independent statistician at Liverpool Clinical Trials Centre (LCTC).

Participant allocations will be irrevocably generated upon completion of the web-based randomisation form by a delegated member of the trial research team. Allocation concealment will be ensured as the service will not release the randomisation code until the participant has been recruited into the trial; this takes place after completion of all baseline measurements.

7.4.8 Intervention arm - SNMES plus usual care

Participants in the SNMES intervention arm will be provided with

- SNMES equipment needed
 - 1 x SNMES device
 - 2 x knee braces
 - 2 x ankle foot orthoses
 - 4 x big electrode pads
 - 4 x small electrode pads
 - 1 x spare 9v battery
- Supporting documentation
 - 1 x SNMES instruction and activity workbook including diary.
 - 1 x Moving more with MS booklet
 - 1 x Chartered Society of Physiotherapy – 6 exercises for staying steady booklet

Participants will be provided with the SNMES device and instructed how to use it. This includes a demonstration and acclimatization session, in which the researcher will go through set up and a series of SNMES cycles on each of the relevant muscle groups with the participant. The session will include instructions on placement of the stimulation pads, fitting the braces and selecting the correct program using the stimulator. The SNMES program will be set up on the device for the participant to use and saved

as a customized setting. The researcher will also discuss how the intervention may be adapted for use at home to ensure intervention fidelity is maintained and participants use the device safely. This will include precautions for using the device and indications for stopping as per instruction manual and workbook. The researcher will show the participant the workbook and signpost them to the section regarding instructions on using the device, study timeline and key dates to help with planning, importance of completing the measures and recording information related to device use, other physical activity and health resources used and support contact information. They will be advised to continue with their normal exercise and physical activity routines and will continue to receive their usual care.

Participants will be encouraged to set individual goals, self-monitor progress and undertake graded increases in SNMES intensity.

Participant set up for use of the SNMES device and maintaining intervention fidelity

The therapeutic effects of SNMES are achieved by the muscle contracting against resistance with the proximal and distal segments orientated at roughly 90 degrees to each other so that the muscle is in its's middle range. For clinical purposes this would be

- Knee joint flexed to 90°
- Ankle joint in neutral or 0°

* For pragmatic purposes a tolerance of up to 30 degrees (in either direction) is permissible at the knee joint and 15 degrees is permissible at the ankle joint i.e.

- Knee joint within 60 to 120 degrees of flexion.
- Ankle joint within 15 degrees of plantar or dorsiflexion

Contractions should be isometric, but it is recognized that some small movement within a constrained range of motion may occur.

It is anticipated that the SNMES program will be carried out with the participant in sitting, however some participants carry out the SNMES program in half or full lying. It is not recommended that participants carry out the SNMES program in standing for safety reasons and risk of falling.

To maintain the joint during the contraction, participants will be provided with knee and ankle braces. In some cases, participants may choose to not use the braces for all exercises, as long as the position of the joint is maintained during contraction.

If participants can sit and rest their feet on the floor, it is likely that the knee braces will not be required. If the participant can progress to an intensity at which the leg moves, despite resting on the floor, then a knee brace should be used.

Assuming the limbs of the participants are contracting against a comfortable and sufficiently soft surface that

1. does not compromise the integrity of the skin,
2. pose a risk of falls or
3. result in excessive movements

adaptations to the participants position should be allowed. Some examples of acceptable modifications to the participant position include:

Lying

Bilateral example

- Participant supine, knees flexed between 60° to 120° with pillows under knee joint, heels supported (either with or without brace)
 - hamstrings contract pulling heels into bed or brace
 - quads contract pulling quads against brace / heavy duvet / blanket over feet
- Participant supine (bed or floor), ankles in neutral, feet flat against surface/ wall (either with or without brace)
 - SNMES causing calves to contract pushing against surface

Seated

Bilateral example

- Participant sitting in chair, with knees flexed to 90° and lower legs against the chair (no brace fitted)
 - hamstrings contracting pulling heels into chair

- Participant sitting in chair, with ankle in neutral, pushing down on both knees or with weight on knees
 - claves to contracting pushing toes into floor

Unilateral examples (lying and sitting)

- In cases where legs are stimulated unilaterally, resistance may be offered by using the other limb. E.g. crossing the non-stimulated leg over or under e.g. quads or hamstring contractions respectively or pushing against the bottoms of the non-stimulated leg e.g. dorsiflexion contraction

Other modifications

In some cases, participants may have access to exercise facilities or equipment which may be used around the ankles or feet to provide resistance to the movement caused by the SNMES e.g. ankle weights.

[figure not shown]
In some cases, the weight of the limb, particularly for knee extension exercises may be sufficient for the resistance required.

The underlying principles regarding Frequency, Intensity, Time and Type are listed in table 2

Table 2 – overview of FITT principles re interventions

Frequency	Participants should aim to stimulate each muscle group at least twice per week. This may be done over 3 to 4 sessions
Intensity	Parameters for the muscle stimulation are: 
 • Pulse frequency: 50Hz • Pulse duration: 450µs • ON:OFF time 5:10 secs • Intensity: maximum tolerated (ma) • Total number of contractions = 45
Time	Each muscle group will take approximately 12 minutes to stimulate. Participants are advised to stimulate 2 muscle groups per session equating to approximately 30 minutes including set up time
Type	Isometric resistance training

The bilateral thigh (quadriceps and hamstrings) and shank (triceps surae and tibialis anterior) muscles will be stimulated. An outline of the pad placements has been provided below.

As per the activities outlined in the workbook, participants will be encouraged to set individual goals, self-

monitor progress and undertake graded increases in SNMES intensity.

Participants will progressively work towards 3 to 4 -sessions per week over a 12-week period with a maximum of 36-sessions in total. The researcher will suggest to participants that they start with aiming for a total of 15 minutes per day so that they get comfortable with the machine and get a sense of achievement.

A suggested program has been identified as per below.

Day 1	Thigh workout 
 • 15 mins bilateral thighs • 15 mins bilateral quads
Day 2	Lower leg workout 
 • 15 mins bilateral tibialis anterior • 15 mins bilateral triceps surae
Day 3	
Day 4	Thigh workout 
 • 15 mins bilateral thighs • 15 mins bilateral quads
Day 5	Lower leg workout 
 • 15 mins bilateral tibialis anterior • 15 mins bilateral triceps surae
Day 6	
Day 7	

However, participants may choose to vary the program to suit their activities and symptoms.

Modifications may include stimulating

- Alternating front and back leg muscles e.g. quads and tib ant one day then hamstrings and triceps surae muscles another
- Stimulating their legs unilaterally e.g. stimulating their left quads and hamstrings together followed by tibialis anterior triceps surae in the same day (co-contractions). They would do the alternative leg the next day and repeat both legs later in the week.

Participants will be contacted after

- the first week and at
- 6-weeks to see how they are getting.

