7.4.6 Clinical measures and exercise testing

7.4.6.1 Lower limb range of movement ROM (Knee and ankle)

Instructions adapted from Tidy's physiotherapy 2003 – Musculoskeletal assessment – Chapter 11 ⁶²

Required equipment (clinician)

- Goniometer
- In some cases visual estimation maybe used e.g.
 - Where the position of the limb is at easily recognizable range of movements such as fully extended = 0°, bent to 90° etc
 - where the range of movement for active is the same as the passive range of movement visual estimation maybe used

Instructions for carrying out the test

- These may be conducted with the participant sitting.
- If a plinth, bed or appropriate piece of equipment is present that allows the participant to lie down in a suitable position for carrying out the measurements.
- The test may be done for up to maximum of 3 times for each movement.
- Active range of movement is completed by the participant moving the joint as much as possible using their own muscles.
- Passive range of movement is completed by the researcher or practitioner moving the joint of the participant as much as possible.

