7.4.6.4 MRC Oxford strength assessment (Knee and ankle)

- The Oxford Scale is a quick method of assessing and grading muscle power.
- The Oxford Scale is a 0-5 scale which is then recorded as 0/5 or 2/5.
- Only whole numbers should be used for the assessment e.g. **no** use of + or - sign qualifiers should be used.
- The researcher should position the participant in the appropriate posture to allow accurate assessment and allow good vision and palpation of the appropriate structures.
- The muscles will be tested isometrically, usually in their mid-range and **NOT** through range.
- The movements being evaluated are
 - Knee extension strength
 - Knee flexion strength
 - Ankle dorsiflexion strength
 - Ankle plantarflexion strength
- This is achieved by positioning
 - Ankle joint in neutral (foot orthogonal to the shank)
 - Knee in 90° of flexion.
- The position of the limb may be adjusted to elicit a better contraction from the muscle group being tested.
- Instruct the participant that you are going to apply some resistance to the limb and that you want them to resist you.
- Verbal encouragement is allowed.
- A maximum of up to three tests are allowed, with the highest value being recorded.
- A score is awarded based on the criteria below

Level	Description
0	No contraction at all
1	Flicker of contraction only (visible/palpable muscle contraction), movement of the joint does not occur
2	movement is possible only with gravity and the weight of the limb counterbalanced
3	Movement against gravity only

4	Movement against gravity with some resistance
5	Movement against gravity with full resistance

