7.4.6.6 Common equipment needed for Timed up and Go and 2MWT (clinical measures)

Required equipment (clinician)

- stopwatch
- two small cones to mark the turnaround points
- worksheets on a clipboard
- a measuring wheel
- telephone
- a source of oxygen
- sphygmomanometer
- automated electronic defibrillator

Required equipment (participant)

- Participants should use their usual walking aids during the test (cane, walker, etc.).

Safety considerations

1. Testing should be performed in a location where appropriate response to an emergency is possible. The appropriate location of a crash cart should be determined by the person supervising the facility.
2. Supplies that must be available include oxygen, sublingual nitroglycerine, aspirin, and albuterol (metered dose inhaler or nebulizer). A telephone or other means should be in place to enable a call for help.
3. The researcher collecting the measurements should be certified in cardiopulmonary resuscitation with a minimum of Basic Life Support. A certified individual should be readily available to respond if needed.
4. Medical doctors are not required to be present during the test. The Principal Investigator after consultation with the wider research team may decide whether attendance by a medical doctor at a specific test is required.
5. If a participant is on chronic oxygen therapy, oxygen should be given at their standard rate or as directed in their medical care plan.

Reasons for immediately stopping a TUG or 2MWT include the following:

1. chest pain,
2. intolerable dyspnea,
3. leg cramps,
4. staggering,
5. diaphoresis (excessive or abnormal sweating for no apparent reason) and
6. pale or ashen appearance.

The researcher must be trained to recognize these problems and the appropriate responses. If a test is stopped for any of these reasons, the participant should sit or lie supine as appropriate depending on the severity or the event and the researcher's assessment of the severity of the event and the risk of syncope. The following should be obtained based on the judgment of the technician: blood pressure, pulse rate, oxygen saturation, and a physician evaluation. Oxygen should be administered as appropriate.

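### Follow-up MRC strength, joint range and Modified Ashworth ratings are open to avoidable observer bias, because the tests leave choices to a tester who is neither masked nor kept apart from device set-up

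*Protocol*

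**What the plan says.** **Who does what.** Section 7.4.8 describes device training by the researcher: "This includes a demonstration and acclimatization session, in which the researcher will go through set up and a series of SNMES cycles". In section 7.4.9 the researcher also takes control participants through their booklet, so this role knows the allocation in both arms.

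Measurement carries the same label. For the Timed up and Go (TUG) and two-minute walk (2MWT), section 7.4.6.6 says: "The researcher collecting the measurements should be certified in cardiopulmonary resuscitation with a minimum of Basic Life Support". For MRC strength, section 7.4.6.4 says: "The researcher should position the participant in the appropriate posture to allow accurate assessment and allow good vision and palpation of the appropriate structures". For passive ROM, section 7.4.6.1 is a little wider: "Passive range of movement is completed by the researcher or practitioner moving the joint of the participant as much as possible". Section 7.4.6.5 (MAS) does not name the tester.

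**Masking.** The only blinding wording in the protocol concerns the coding of interview transcripts (section 9.2.2).

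**Latitude in the tests.**
- MRC strength (7.4.6.4): "Verbal encouragement is allowed"; "The position of the limb may be adjusted to elicit a better contraction from the muscle group being tested"; "A maximum of up to three tests are allowed, with the highest value being recorded".
- ROM (7.4.6.1): up to three attempts per movement. Visual estimation is permitted in some cases, either at easily recognised positions or "where the range of movement for active is the same as the passive range of movement visual estimation maybe used".
- MAS (7.4.6.5): up to three attempts per muscle group.

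Neither the ROM nor the MAS section says which attempt is recorded.

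**The concern.** Participants in a device-versus-usual-care comparison cannot be masked, so protection against observer bias has to come from the assessor or from the rigidity of the test. For these three measures the protocol provides neither. A tester who knows the allocation may decide how much to encourage, whether to shift the limb, whether to try again, and whether to read the goniometer or judge by eye. None of this need be deliberate.

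Sections 5.1 and 9.2.1 say the outcome data will inform the choice of primary outcome and the sample size of a definitive trial. Muscle weakness is the first clinical target named in the aim (section 5), and MRC grading is the strength measure in Table 1. If observer effects make a loosely specified measure look more responsive than a tightly specified one, that choice could be misled. A later analysis plan could not repair this, because it arises when the test is performed.

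**Working it through.** The protocol states no figure on this point, so the check is mainly a reading of the sections against each other.

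**1. Count the outcomes measured at follow-up.** Table 1 (section 7.4.2) has 15 rows ticked at 12 weeks and 6 months: EDSS, TUG, 2MWT, PSFS, MSIS-29, FSS, MFIS-5, WHODAS, EQ-5D-5L, ModRUM, pain rating, MRC, ROM, MAS and walking aids.

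**2. Remove those completed by the participant.** These are PSFS, MSIS-29, FSS, MFIS-5, WHODAS, EQ-5D-5L, ModRUM and pain, which is 8. That leaves 15 − 8 = 7 that staff rate, time or record.

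**3. Ask which of the 7 give the tester the latitude described.**

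| Measure | Latitude in the protocol |
|---|---|
| MRC strength (7.4.6.4) | Encouragement unscripted; limb may be adjusted; 1–3 attempts, best kept |
| ROM (7.4.6.1) | Up to 3 attempts, no recording rule; visual estimation in some cases |
| MAS (7.4.6.5) | Up to 3 attempts, no recording rule |
| TUG (7.4.6.7) | Scripted instructions, stopwatch |
| 2MWT (7.4.6.8) | Scripted encouragement, all other encouragement excluded |
| Walking aids (7.4.4.4) | Tick list |
| EDSS (7.4.4.1) | Descriptor table; no rater named and none of these permissions given |

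So the absence of masking covers 7 of 15 rows, but absence of masking together with granted discretion covers 3 of 15.

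**4. Direction for MRC.** With k attempts the recorded grade is max(g₁, …, g_k), which cannot fall as k rises. The rule is the same in both arms on paper, but the tester chooses k from 1 to 3. If k tends to be larger in one arm, that arm's recorded grades rise with no change in strength. For ROM and MAS the direction is undefined, because no rule selects the value.

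**5. When it can happen.** Section 7.4.7 releases the allocation only after all baseline measurements. Baseline ratings therefore cannot follow allocation. The 12-week and 6-month ratings can, so any drift enters the change from baseline.

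**6. Could the study see it afterwards?** Section 9.1.1 gives 50 × (1 − 0.20) = 40 participants with data, which is 20 per arm if losses are equal (assumed). The 95% half-width for a between-arm difference in SD units is about 1.96 × √(2/20) = 0.62. A modest observer effect would be invisible within that.

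**The case against.** The strongest reply is that this is a descriptive feasibility study. Section 9.1.1 disclaims a comparative sample size calculation, and the progression criteria in section 9.2.1 are consent, retention and adherence, none of them assessor-rated. The protocol does not say that the primary outcome will be chosen on apparent between-arm response. Interviews ask participants which outcomes matter (7.4.10.1), and patient partners helped select the measures (10.3). A uniform shift in one arm would also leave the within-arm SD, a main input to a sample size, unchanged. All of this stands and keeps the point modest. It does not remove it, because outcome selection and parameter estimates are stated objectives, and discretion used unevenly within an arm would alter the SD as well.

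Several stronger readings are tempting but unsupported:
- **One person does both jobs.** The text shows a shared, generic role label across two sites. It also mentions a practitioner for passive ROM. It does not say that one individual trains and tests the same participant, only that nothing keeps the tasks apart.
- **All seven staff-assessed outcomes are affected alike.** The walking tests are scripted or timed, and encouragement and limb adjustment are permitted for MRC only.
- **Visual estimation freely replaces the goniometer.** It is limited to stated kinds of case.
- **The study has no recording rule for ROM or MAS.** The protocol has none. Appendix 1 lists a separate outcome measure and clinical test pack, not among the documents reviewed, which may contain one.
- **A second assessor is already available.** Section 7.2.2 names the local research team and research assistant for recruitment calls. That does not show they are qualified or free to test.

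**Conclusion.** The point holds for follow-up MRC strength, ROM and MAS: 3 of 15 follow-up outcomes, at 12 weeks (marked as the primary endpoint in Table 1) and 6 months. These ratings are open to observer bias that fixed test rules would largely prevent. It is not shown that they will be biased.

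The size is unknown. The documents give no SD, effect size or rater-agreement figure, so a reader should not infer a particular grade shift or a particular loss of power in the future trial; either would rest on invented inputs. The conclusion rests on the protocol text as it stands and on the possibility that testers know the allocation, which nothing in the protocol prevents. The feasibility decision on consent, retention and adherence is unaffected. This is a low-cost improvement worth making, not a fault that undermines the study.

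**What to change.** **Tighten the test rules** in sections 7.4.6.1, 7.4.6.4 and 7.4.6.5, and identically in the clinical test pack:
- set a fixed number of attempts for MRC, ROM and MAS, and state which value is recorded;
- script the MRC encouragement, as the 2MWT already does;
- record the limb position used at baseline and reuse it at both follow-ups;
- use the goniometer for every ROM value.

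This is a wording change. Its cost is slightly longer testing and less flexibility for fatigued participants.

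**Separate the tasks where possible.** In section 7.4.2, state that, where existing site staff allow, the 12-week and 6-month tests are done by someone who did not deliver that participant's set-up session. Add one CRF item recording whether the assessor knew the allocation. This should not require extra staff; where no second person is free, the CRF item shows it. The item also gives the definitive trial a simple count of how often assessors did not know the allocation.

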9.2 DATA ANALYSIS

9.2.1 Quantitative analysis

Descriptive statistics will be used to summarise data in respect to study objectives and outcome measures as outlined below.

- Estimating screening, recruitment and attrition rates.
- Collecting data on candidate outcome measures to determine the primary outcome for the future trial and enable sample size calculations based on this.
- Determining intervention acceptability.
- Evaluating the feasibility and acceptability of health economics measures.

Feasibility progression criteria

Programme criteria using a traffic light system, along with outcome measures and qualitative data will guide decisions about whether a future definitive trial is feasible and warranted and identify any required amendments.⁷⁶

Outcome	Green: feasible with minimal or no modifications	Amber: feasible with moderate modifications	Red: major modifications required/ limited feasibility.
Consent rates	>50%	30-50%	<30%

(of eligible people)			
Retention at 6 months	>80%	60%-80%	<60%
Intervention adherence	≈ 22 sessions or more	≈ 10-21 sessions	≈ 9 sessions or fewer

Health economic component

The aim of the future trial will be to determine the effectiveness and cost-effectiveness of SNMES. This study will provide preliminary data for a descriptive analysis of quality-of-life measures, main cost drivers and differences between groups. It will inform preparatory work regarding rudimentary cost-effectiveness or value of information analysis and data collection methods for resource use and economic evaluation in the definitive trial. Overall levels of data completeness will also be evaluated.

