changed the order and structure of how things are presented to people in the study such as use of a single rather than multiple consent sheets. They have also been involved in helping to sense check our recruitment and retention strategy, ensuring that it is appropriate for people with MS e.g. emphasis on needing to stay in the study was clear and not too forceful.

PPIE also helped us in developing the intervention and control arm components of the study.

Control arm

PPIE suggested better standardising the resources that are normally included as a part of usual care. This was also identified as being an important part of our retention strategy. PPIE expressed that even if participants were aware that they might not get the SNMES they would more likely drop out if they didn't receive anything as a part of the study. This was discussed in the PPI discussion in development of the application, and it was identified that more information may be helpful to participants. However, participants felt the potential for drop out after being randomised to the control group would not be offset by providing more information or further expanding on why we could not give everyone in the study a device either later in the study. The PPI group suggested resources that they have been given as a part of their usual care and this was also checked with the usual care given at the study sites

SNMES arm

Participants helped us to make the SNMES programme simpler for people to follow. PPI identified it would be good to give participants a rough plan to follow that could then be adapted based on how they felt. They also suggested keeping it simple, for example thigh muscles one day and then lower leg muscles the next. Previously participants would have been required to rotate different muscles between the thigh and lower leg. We have had to increase the overall number of days from 3 to 4, however the total number of times and duration for each muscle that needs to be stimulated has remained the same.

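### The 36-session maximum does not fit the suggested four-day week (48 sessions in 12 weeks), and the adherence limits are bare counts with no stated denominator

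*Protocol*

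**What the plan says.** **Total and weekly target.** Section 7.4.8 states: "Participants will progressively work towards 3 to 4 -sessions per week over a 12-week period with a maximum of 36-sessions in total".

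**Table 2 (section 7.4.8).** On frequency: "Participants should aim to stimulate each muscle group at least twice per week. This may be done over 3 to 4 sessions". On time: "Participants are advised to stimulate 2 muscle groups per session equating to approximately 30 minutes including set up time".

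**Muscles.** The same section names four groups: "The bilateral thigh (quadriceps and hamstrings) and shank (triceps surae and tibialis anterior) muscles will be stimulated".

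**Weekly plan.** It is introduced with "A suggested program has been identified as per below" and puts sessions on Days 1, 2, 4 and 5, leaving Days 3, 6 and 7 empty. The text after it lets participants vary the plan to suit their activities and symptoms, and describes a one-leg-at-a-time alternative. Participants are advised to begin with 15 minutes a day.

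**History of the plan.** Section 10.3, on the SNMES arm, says: "We have had to increase the overall number of days from 3 to 4". The sentence goes on to say that how often and how long each muscle is stimulated did not change.

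**Adherence limits.** Section 9.2.1 sets green at approximately "22 sessions or more", amber at about 10 to 21 and red at about 9 or fewer. No total is given against which these counts are to be read. Section 9.1.1 plans precision around an adherence rate of 60% in 40 participants.

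**The concern.** Section 7.4.8 gives a ceiling that matches three sessions a week and a printed week that has four. Both cannot hold for a participant who follows the printed week throughout, and nothing says what happens when the ceiling is reached early.

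The consequence for the analysis lies in the traffic light. Adherence is one of three progression criteria, and its limits are session counts whose meaning depends on the intended total. If that total is unsettled, the same count can be read as a majority of the programme or as less than half of it. A later choice of denominator, made with the data in view, could change how adherence is described to those planning the definitive trial. Sessions are also counted alike whatever their length, so a 15-minute starter session scores the same as a full session of about 30 minutes.

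**Working it through.** **Inputs.** From section 7.4.8: 12 weeks, 3 to 4 sessions a week, maximum 36, four muscle groups, a minimum of two stimulations per group per week, two groups advised per session, four session days in the suggested week. From section 9.2.1: limits at 22, 10 and 9 sessions. From section 9.1.1: 60% adherence, n = 40, stated half-width 15 points.

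**1. Reproduce the stated maximum.**
- 3 per week × 12 weeks = 36, which matches the protocol.
- 4 per week × 12 weeks = 48, which exceeds it by 12.

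**2. Sessions implied by Table 2.**
- 4 groups × 2 per week = 8 group-stimulations a week.
- 8 ÷ 2 groups per session = 4 sessions a week, or 48 in 12 weeks.
- Over 12 weeks: 8 × 12 = 96 group-stimulations.
- 36 sessions × 2 groups = 72, and 72 ÷ 96 = 75%. Per group per week this is 72 ÷ (4 × 12) = 1.5, below the Table 2 minimum of two.
- To deliver 96 within 36 sessions would take 96 ÷ 36 = 2.67 groups per session, more than the advised two.

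**3. Timing under the suggested week, followed from week 1.**
- Maximum reached: 36 ÷ 4 = 9 weeks.
- Green count reached: 22 ÷ 4 = 5.5 weeks. At three sessions a week it would be 22 ÷ 3 = 7.3 weeks.

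**4. The limits against each possible total.**

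| Limit (sessions) | Of 36 | Of 48 |
|---|---|---|
| Green, 22 | 61.1% | 45.8% |
| Lower end of amber, 10 | 27.8% | 20.8% |
| Upper end of red, 9 | 25.0% | 18.8% |

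**5. Which total do the limits fit?**
- 0.60 × 36 = 21.6, which rounds to 22.
- 0.60 × 48 = 28.8, which rounds to 29.
- 0.25 × 36 = 9, the top of red.

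The counts fit 36 and do not fit 48.

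**6. Side check of the 60% in section 9.1.1.** 1.96 × √(0.6 × 0.4 ÷ 40) = 15.2 points, which agrees with the stated 15. That figure is sound as a binomial precision. The section does not say that the 60% is a share of sessions.

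**7. Can a build-up reconcile 36 with four days?** Six weeks at 2 a week and six weeks at 4 give 12 + 24 = 36. Such a schedule is arithmetically possible, but none is written down. The starting advice limits minutes per day and does not set a smaller number of session days.

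**The case against.** The strongest reply is that 48 is not a prescription. The text speaks of building up to three or four sessions, Table 2 expressly allows three, two groups per session is advice, and the printed week is a suggestion that may be varied. Three sessions a week with more than two groups in some of them would satisfy both Table 2 and the maximum. Section 10.3 says that the work per muscle was left unchanged when the days increased. All of this stands, and it makes the 46% and the 75% conditional. It does not remove the conflict: the only week the protocol prints, followed for the full period, breaks the stated maximum.

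Four stronger readings are tempting, and the documents do not support them.

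- **That the limits were set on 36 and never updated.** Section 9.2.1 names no denominator. The fit to 60% of 36 is close, but it is an inference.
- **That a participant can stop at 5.5 weeks and be classed green.** Section 9.2.1 does not say that the limits classify individuals, nor how counts are combined across participants.
- **That the count alone decides progression.** The traffic light is to guide the decision together with outcome measures and qualitative data.
- **That one-leg sessions are over-credited.** The alternative in section 7.4.8 stimulates four groups on one leg in a day. That is 4 × 1 = 4 leg-muscle stimulations, the same as 2 groups × 2 legs = 4.

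It can also be said that the definition of a countable session belongs in the statistical analysis plan, which is not at hand. That is fair for the definition. The maximum, the printed week and the numerical limits, however, are all fixed in the protocol.

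**Conclusion.** The point holds as an internal contradiction with a consequence for one progression criterion. The 36-session maximum equals three a week. The suggested week, and Table 2 at the advised two groups per session, both lead to four a week and 48 in total.

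The green limit is 61% of the stated maximum and 46% of the full four-day programme. The 46%, the 5.5 weeks and the 9 weeks assume that the four-day week is followed from week 1. The 72 against 96 group-stimulations also assumes two groups in every session. Under the protocol's own maximum the green limit is a reasonable majority of sessions.

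The fault is therefore that the limit cannot be interpreted until the total is settled. Whether it is too low depends on that total.

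**What to change.** 1. Reconcile the maximum, Table 2 and the suggested week in section 7.4.8 with the account of the change in section 10.3. Which schedule applies is for the clinical team.
2. Then, before any adherence data are seen, restate the limits in section 9.2.1 as percentages of the reconciled total, with the matching counts beside them. For example, a 60% limit is 22 of 36 or 29 of 48.
3. Define a countable session, so that a 15-minute starter session does not score the same as a full one. If stimulations are counted instead, count them per leg and muscle, so that the permitted one-leg sessions receive full credit.

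**Cost.** Wording changes to the protocol and the workbook. The diary may need changing too, because the documents do not show whether it records muscle and leg. If the total settles above 36, green will be harder to reach.
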